6.3.2.4. Per Protocol (PP) Population

For the analyses at Visit 4 (Week 12), the PP population includes all randomized subjects who met all inclusion/exclusion criteria at enrollment, complied with the assigned study product, and were followed up until the first diagnosis of BV or through Visit 4 (Week 12).

For the analyses at Visit 7 (Week 24), the PP population includes all randomized subjects who met all inclusion/exclusion criteria at enrollment, complied with the assigned study product, and were followed up until the first diagnosis of BV or through Visit 7 (Week 24).

In the unlikely event of an error in randomization or study product administration (i.e., incorrect product), subjects will be grouped by the product they actually received.

Subjects who terminate early prior to the visit of interest for reasons other than lack of treatment effect with no positive result at another visit, as well as subjects with a missing or non-evaluable Amsel or Nugent result with no positive result at another visit, are excluded from the PP population.

6.3.2.5. Blinded Review of Efficacy Analysis Population Eligibilities

Prior to unblinding, a blinded case review committee will review subjects with a reported concomitant infection/disease/procedure that may interfere with study product, use of concomitant medications or products that may interfere with study product, significant protocol deviations, and other events that may impact study product effectiveness or study analyses. On a case-by-case basis, the case review committee will determine if each subject will be included in the various efficacy analysis populations, if and when a subject should be censored or removed from any analyses, and/or any other analytical requirements for the subject. The committee will be blinded to both treatment assignment as well as BV outcome status. The protocol denotes that the committee will only review subjects for inclusion into the PP population, however all efficacy populations will be considered.

6.3.2.6. Analysis Population Summaries

Table 5 summarizes the ITT and mITT analysis population eligibilities by randomized treatment group and reasons excluded. Table 6 summarizes the Safety, CC, and PP analysis population eligibilities by actual treatment group and reasons excluded. Subjects will be included in the count for a particular reason for exclusion if they met that criterion. As subjects may meet more than one criterion for exclusion, the “Excluded from...” counts may be less than the sum of the individual reason counts. A listing of the subjects excluded from each of the analysis populations and the reasons for exclusion will be provided (Listing 1). A listing of subjects whose assigned treatment group does not match their randomized treatment group will be provided in Listing 2.

6.4. Covariates and Subgroups

The protocol does not define any formal subgroup hypothesis tests, and the study is not adequately powered to perform formal subgroup hypothesis testing. However, safety and enrollment summaries will be presented by clinical site. In addition, summaries of colonization will be presented by subgroups defined by menses and sexual intercourse variables (see Section 8.2).

6.5. Missing Data

The primary efficacy outcome measure of BV recurrence will be assessed in the CC population. Use of the mITT population has previously been recommended by the FDA where missing values from subjects who drop out early are imputed using Last Observation Carried Forward (LOCF) [6]. However, this includes subjects who dropped out after completing at least one-follow-up visit, and/or before their first positive diagnosis. LOCF would classify such subjects as ‘not recurrent.’ Thus, it is possible that the estimated proportions of treatment successes in a study arm could, in reality, be larger than expected. Thus, LOCF could result in an over-optimistic estimate of treatment effect, conflicting with the following rationale for using an ITT analysis population stated in ICH E9 [7]: “[ITT analysis] tends to avoid over-optimistic estimates of efficacy resulting from a per protocol analysis, since the non-compliers included in the [ITT] analysis set will generally diminish the estimated treatment effect.” In addition, simulation studies suggest that CC analysis leads to slightly less biased estimates of the difference in cure proportions (LACTIN-V vs. placebo) compared to the mITT analysis using LOCF.

To assess the effect of the choice of analysis population on the primary analysis, the analysis will be repeated as a secondary analysis in the ITT, mITT, and PP populations. The following imputation methods will be used for BV recurrence by Visit 4 and BV recurrence by Visit 7 in the ITT and mITT populations:

- LOCF
- Worst-Case Scenario – impute missing/unevaluable values in the LACTIN-V group as treatment failures and missing values in the Placebo group as treatment successes.

For summaries of recurrence in “by study day” displays, missing data will not be imputed.

For the secondary analyses of successful *L. crispatus* colonization by Visit 4 and by Visit 7, missing or unevaluable colonization data at a visit will imputed as unsuccessful colonization. For summaries of colonization in “by study day” displays, missing data will not be imputed.

6.6. Interim Analyses and Data Monitoring

The study is monitored to determine if any of the safety halting rules are met.

-
1. One or more subjects experience a treatment-related SAE.
 2. Two or more subjects experience treatment-related vulvar and/or vaginal ulceration, abscess, or necrosis.
 3. Four or more subjects experience a treatment-related severe (Grade 3) systemic adverse event.
 4. An overall pattern of symptomatic, clinical, or laboratory events that the DMID, medical monitor, or DSMB consider associated with study product and that may collectively represent a serious potential concern for safety.

If any of the halting rules are met, the study will not continue with the remaining enrollments or study treatments without a review by and recommendation from the DSMB to proceed. A summary of halting rules is provided in [Table 7](#).

The DSMB met to review aggregate safety data on 02JUN2017 after one third of the 228 subjects completed Study Visit 2 (Week 4). The DSMB may also review study progress and subject safety data at other specified times during the course of the study and hold a study closeout meeting, as defined in the DSMB Charter. No interim analyses of efficacy data are planned and this Statistical Analysis Plan does not cover the interim safety analyses.

6.7. Multicenter Studies

Safety and efficacy data will be pooled across all clinical sites. Center effects are not anticipated because treatment is self-administered, the sites are using standardized procedures for assessment of unsolicited adverse events, and the study relies on a central laboratory for Gram stain Nugent scoring. See Sections 8 and 9 for more details.

6.8. Multiple Comparisons/Multiplicity

As this trial is designed to provide screening evidence about safety and efficacy for a subsequent Phase III trial and is not a confirmatory trial, no adjustments for multiplicity are planned.

7. STUDY SUBJECTS

7.1. Disposition of Subjects

The disposition of subjects in the study will be tabulated by randomized treatment group and all subjects. [Table 8](#) shows the number of subjects who are screen failures and the number of subjects that met each inclusion/exclusion criterion. The number of enrolled subjects in the study completing study milestones will be tabulated separately by randomized treatment group. [Table 9](#) shows the total number of subjects enrolled, randomized, treated, complying with treatment, and completing each visit (Visit 1 through Visit 7). A listing of subjects who completed the study, terminated early from study, or discontinued treatment and the reason for early termination or treatment discontinuation is included in [Listing 3](#).

[Figure 1](#) is a flowchart showing the disposition of study subjects in the safety and efficacy analyses, adapted from the CONSORT statement. It shows the number of subjects eligible, enrolled and randomized, lost to follow-up, and analyzed for the safety and efficacy analyses, overall and by treatment group.

7.2. Protocol Deviations

A summary of subject-specific protocol deviations will be presented by the deviation category, the type of deviation, and randomized treatment group for all enrolled subjects ([Table 10](#)). All subject-specific protocol deviations and non-subject-specific protocol deviations will be included in Appendix III as data listings ([Listing 4](#) and [Listing 5](#), respectively).

8. EFFICACY EVALUATION

8.1. Primary Efficacy Analysis

For the primary analysis, the cumulative proportion of BV recurrence by Visit 4 (Week 12) will be summarized by treatment group. A formal hypothesis test will be performed with null hypothesis that the cumulative proportion of BV recurrence by Visit 4 (Week 12) in the LACTIN-V group is equal to that in the placebo group and alternative hypothesis that they are not equal. Cumulative proportion of BV recurrence is defined as follows: the numerator is the number of subjects who experience recurrence at least once through Visit 4 in the particular analysis population and the denominator is the number of subjects included in the particular analysis population. [Table 11](#) will present the cumulative proportion of BV recurrence by Visit 4 (Week 12) (and 95% Wilson confidence interval) in each treatment group along with the odds ratio of BV recurrence proportions between treatment groups (and 95% asymptotic confidence interval). The p-value from the Chi-Square test will be presented. The summaries will be calculated in the ITT, mITT, CC, and PP populations, where the ITT and mITT summaries will be replicated using the imputation methods described in Section 6.5. [Listing 6](#) will present individual efficacy data for all subjects.

8.2. Secondary Efficacy Analyses

[Table 12](#) will present the cumulative proportion of BV recurrence by Visit 7 (Week 24) (and 95% Wilson confidence interval) in each treatment group along with the odds ratio of BV recurrence proportions between treatment groups (and 95% asymptotic confidence interval). A formal hypothesis test will be performed with null hypothesis that the cumulative proportion of BV recurrence by Visit 7 (Week 24) in the LACTIN-V group is equal to that in the placebo group and alternative hypothesis that they are not equal. The p-value from the Chi-Square test will be presented. The summaries will be calculated in the ITT, mITT, CC, and PP populations, where the ITT and mITT summaries will be replicated using the imputation methods described in Section 6.5. [Table 13](#), [Table 14](#), [Table 15](#), and [Table 16](#) will present BV recurrence by study visit (Day 28, 56, 86, and 168). For the by-visit summaries, the proportions of subjects with BV recurrence at a visit is defined as follows: the numerator is the number of subjects who experience recurrence at the particular visit and the denominator of the proportion of subjects with BV recurrence is the number of subjects in the analysis population who returned for the visit. The 95% Wilson confidence interval for the proportion in each treatment group along with the odds ratio of BV recurrence proportions between treatment groups (and 95% asymptotic confidence interval) and the p-value from the Chi-Square test will also be presented.

As an additional analysis of the outcome measures of BV recurrence by Visit 4 and by Visit 7, the median time to BV recurrence (from randomization) will be estimated by treatment group using Kaplan-Meier estimates ([Table 17](#) and [Table 18](#)). In addition, the median 95% confidence interval, minimum, first quartile, third quartile, and maximum estimates of time to BV recurrence will be presented. For subjects who experience BV recurrence by Visit 4 (Week 12), the time of BV recurrence will be defined as the midpoint between the earliest time point of a positive BV diagnosis (post-baseline) and the previous observed time point. For subjects without BV recurrence at or before Visit 4, the BV recurrence endpoint will be coded as censored, with time to recurrence defined as the elapsed time from the first dose of study product, to the Visit 4 time point, or to the first occurrence of loss to follow-up or the time-point at which the subject became ineligible for the particular analysis population. Time to BV recurrence by Visit 7 (Week 24) will be defined similarly. The analyses will be performed in the ITT, mITT, CC, and PP populations, where the ITT and mITT summaries will be replicated using the imputation methods described in Section 6.5. Kaplan-Meier curves for BV recurrence will also be generated for each analysis population by Visit 4 (Week 12) and by Visit 7 (Week 24), respectively ([Figure 2](#) and [Figure 3](#)).

As a sensitivity analysis of the outcome measures of BV recurrence by Visit 4 and by Visit 7, the cumulative proportion of BV recurrence analyses will be repeated in the mITT and CC populations after removing the subjects who received additional treatment for BV as documented in the concomitant medications CRF after the beginning of administration of LACTIN-V or placebo and before Visit 4 and before Visit 7, respectively (Table 19 and Table 20).

Table 21 will present the proportion of subjects who experience successful *L. crispatus* colonization at any time post-baseline through Visit 4 (Week 12) (and 95% Wilson confidence interval) in each treatment group along with the odds ratio of *L. crispatus* colonization (and 95% asymptotic confidence interval). A formal hypothesis test will be performed with null hypothesis that the proportion subjects who experience successful *L. crispatus* colonization through Visit 4 (Week 12) in the LACTIN-V group is equal to that in the placebo group and alternative hypothesis that they are not equal. The p-value from the Chi-Square test will be presented. The analyses will be performed in the ITT, mITT, CC, and PP populations, where the ITT and mITT summaries will use the imputation methods described in Section 6.5. Table 22 presents the same summaries for successful *L. crispatus* colonization at Visit 7 (Week 24). Table 23, Table 24, Table 25, and Table 26 present *L. crispatus* colonization by study visit (and 95% Wilson confidence interval) in each treatment group along with the odds ratio of *L. crispatus* colonization (and 95% asymptotic confidence interval). A formal hypothesis test will be performed with null hypothesis that the proportion of subjects who experience successful *L. crispatus* colonization through each visit in the LACTIN-V group is equal to that in the placebo group and alternative hypothesis that they are not equal. The p-value from the Chi-Square test will be presented. Table 27, Table 28, Table 29, and Table 30 presents summary statistics of the concentration of *L. crispatus* CTV-05 by study visit.

Table 31, Table 32, Table 33, and Table 34 will present *L. crispatus* colonization by study day, treatment group, and number of condom-less sexual intercourse acts for each analysis population. The proportion of subjects with colonization along with the 95% Wilson confidence intervals will also be presented. Number of condom-less sexual intercourse acts will be broken up by quartiles from data obtained from the sexual history interview. If the distribution of sexual intercourse acts is such that the use of quartiles does not lead to distinct intervals of values, other cutpoints will be examined (e.g. tertiles, above/below median). Figure 10, Figure 11, Figure 12, and Figure 13 will present *L. crispatus* CTV-05 concentration by study visit, treatment group, number of condom-less sexual intercourse acts, and analysis population.

Table 35, Table 36, Table 37, and Table 38 will present *L. crispatus* colonization by study day, treatment group, and number of partners for each analysis population. Number of partners will be categorized as “No partners,” “1 Partner,” and “>1 Partner” from data obtained from the sexual history interview. Depending on the distribution of number of partners, other cutpoints may be examined. Figure 14, Figure 15, Figure 16, and Figure 17 will present *L. crispatus* CTV-05 concentration by study visit, treatment group, number of partners, and analysis population.

Summaries of days since last dose (mean, median, standard deviation, range) will be presented by *L. crispatus* colonization status will be presented in Table 39, Table 40, Table 41, and Table 42. *L. crispatus* CTV-05 concentration and time since last dose will be presented graphically for each visit, treatment group, and analysis population in Figure 6, Figure 7, Figure 8, and Figure 9. A smoothing spline regression model will be fit with treatment group as an independent variable. The fitted curves with 95% confidence bands will be included in the figures. Model fit and inference of the parameters will be commented on in the final report but not included in a table.

L. crispatus colonization will be presented by treatment compliance status in Table 43, Table 44, and Table 45. Treatment compliance will be categorized as “Compliant” or “Not compliant,” and will be assessed from the start of treatment administration up until the visit listed. See Section 9.2 for measurements of

treatment compliance. Box plots of *L. crispatus* CTV-05 concentration by treatment compliance status are provided for each treatment group, visit, and analysis population in [Figure 18](#), [Figure 19](#), and [Figure 20](#).

Summaries of days since the last day of the last menstrual period (mean, median, standard deviation, range) by *L. crispatus* colonization status will be presented in [Table 46](#), [Table 47](#), [Table 48](#), and [Table 49](#).

Occurrence of menses will be captured on the memory aid. *L. crispatus* CTV-05 concentration and time since last day of the last menstrual period will be presented graphically for each visit, treatment group, and analysis population in [Figure 21](#), [Figure 22](#), [Figure 23](#), and [Figure 24](#). A smoothing spline regression model will be fit with treatment group as an independent variable. The fitted curves with 95% confidence bands will be included in the figures. Model fit and inference of the parameters will be commented on in the final report but not included in a table.

L. crispatus colonization will be also be presented by occurrence of menses after the last dose taken in [Table 50](#), [Table 51](#), [Table 52](#), and [Table 53](#). Subjects will be categorized as menstruating after their last dose taken before the visit presented, or not menstruating after the last dose taken before the specified visit. If there are less than three subjects in either treatment group who had menses since their last dose for a specified visit, that visit will be excluded from the table. Box plots of *L. crispatus* CTV-05 concentration by occurrence of menses are provided for each treatment group, visit, and analysis population in [Figure 25](#), [Figure 26](#), [Figure 27](#), and [Figure 28](#).

For all by-visit summaries, the proportions of subjects with colonization at a visit is defined as follows: the numerator is the number of subjects who experience recurrence at the specified visit and the denominator of the proportion of subjects with BV recurrence is the number of subjects in the analysis population and subgroup who returned for that visit.

As an additional analysis of the colonization analyses, the median time to colonization (from randomization) will be estimated by treatment group using Kaplan-Meier estimates ([Table 54](#)). In addition, the median 95% confidence interval, minimum, first quartile, third quartile, and maximum Kaplan-Meier estimates of time to BV recurrence will be presented. For subjects who experience colonization by Visit 4 (Week 12), the time of colonization will be defined as the midpoint between the earliest time point of colonization (post-baseline) and the previous observed time point. For subjects without colonization at or before Visit 4, the colonization endpoint will be coded as censored, with time to colonization defined as the elapsed time from the first dose of study product, to the Visit 4 time point, or to the first occurrence of loss to follow-up or the time-point at which the subject became ineligible for the particular analysis population. Time to colonization by Visit 7 (Week 24) will be defined similarly. Kaplan-Meier curves for colonization will also be generated ([Figure 4](#) and [Figure 5](#)).

[Table 55](#) will present the proportion of subjects who were compliant (See Section 3.3.5) with the dose regimen through their first BV recurrence or through Visit 4 (Week 12) (and 95% Wilson confidence interval) in each treatment group with difference in compliance proportions between treatment groups (and 95% Wilson confidence interval). The summaries will be presented in the ITT, mITT, and CC populations. The p-value from the Chi-Square test will also be presented. [Table 56](#), [Table 57](#), [Table 58](#), [Table 59](#), [Table 60](#), [Table 61](#), and [Table 62](#) will present summaries of product administration via subject report, returned applicators, and staining for each week. Summaries will be presented by clinical site and treatment group. [Listing 7](#) and [Listing 8](#) will present individual dosing data.

The responses to the acceptability questionnaire at screening and at Visit 4 (Week 12) will be summarized by treatment group. For categorical responses, the proportion of subjects with the particular response and its associated 95% Wilson confidence interval will be used ([Table 63](#) and [Table 64](#)). For continuous or discrete responses, the mean, standard deviation, median, and range of responses will be used ([Table 65](#) and [Table 66](#)).

The analyses will be performed in the ITT, mITT, CC, and PP populations. Individual responses will be included in [Listing 9](#).

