5. SAMPLE SIZE CONSIDERATIONS

Sample size calculations are based on the assumption of detecting a 50% reduction in the cumulative proportion of subjects who experience BV recurrence by 12 weeks post-administration of study product among subjects receiving LACTIN-V compared to those receiving placebo in a complete case analysis at the 0.05 significance level. The proportion of subjects among controls who will experience BV recurrence at 12 weeks is assumed to be 30%. We assume a LACTIN-V to placebo allocation ratio of 2:1 and 10% of subjects drop-out from the Complete Case population. Given logistical and feasibility constraints on the sample size and that this is a Phase II-b trial, which will provide screening evidence about safety and efficacy for a subsequent Phase III trial, this trial is powered at the 70% level. Given the assumptions above, a sample size of 228 subjects is required to detect a 50% reduction in the cumulative proportion of subjects experiencing recurrence in the Complete Case population with 70% power using the Pearson Chi-Square test.

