6. GENERAL STATISTICAL CONSIDERATIONS

6.1. General Principles

Tabulations will be used extensively to summarize the data. All continuous variables will be summarized using the following descriptive statistics: n (sample size), mean, standard deviation, median, maximum, and minimum. The frequency and percentages (based on the sample size) of observed levels will be reported for all categorical measures. Wilson confidence intervals for binomial proportions and differences in binomial proportions will be computed for efficacy variables. Blaker confidence intervals for binomial proportions and differences in binomial proportions will be computed for safety variables. For the hypothesis tests comparing treatment groups with respect to safety outcomes, the two-sided Fisher's Exact test will be used. For the hypothesis tests comparing treatment groups with respect to efficacy outcomes, the two-sided Chi-Square test will be used. For all tests, a 5% two-sided significance level will be used.

For all efficacy outcome measures, the Complete Case population (see Section 6.3) will be used as the primary analysis population and the Per Protocol, modified Intent-to-Treat, and Intent-to-Treat populations will be used as secondary analysis populations. For all safety analyses, the Safety population will be used as the analysis population.

All summary tables will be structured with a column/sub-table for each treatment group (LACTIN-V, Placebo, and All Subjects). In general, all data will be listed by treatment group and/or subject, and when appropriate by visit number within subject. The total population size relevant to that table/column if applicable, including any missing observations will be displayed in the tables.

Note that in the data listings, Subject ID is the unique subject identifier, not the Study ID used on study and dates will not be included, only Study Day. Study Day 1 will be the day of the first dose of treatment.

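### The time-to-recurrence analysis has no between-arm comparison, and at the planning rates its 12-week median cannot be estimated in either arm

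*SAP*

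**What the plan says.** Protocol 11.6.4.1 and 11.6.4.2 promise secondary time-to-event analyses of BV recurrence by Visit 4 and by Visit 7, and leave the details to the SAP. SAP 8.2 supplies them: "the median time to BV recurrence (from randomization) will be estimated by treatment group using Kaplan-Meier estimates". It adds the confidence interval for the median, the minimum, the quartiles, the maximum, and Kaplan-Meier curves in four populations (Tables 17 and 18, Figures 2 and 3).

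On dating, "the time of BV recurrence will be defined as the midpoint between the earliest time point of a positive BV diagnosis" and the previous observed time point. The pseudo-code in SAP 6.1.1 stratifies by treatment but keeps only the censoring summary and the quartiles. The Table 17 shell, whose format Table 18 shares, has a row for number and percentage with recurrence. It has no row for a difference, hazard ratio or p-value.

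The only planning rates are in SAP 5: "The proportion of subjects among controls who will experience BV recurrence at 12 weeks is assumed to be 30"%, with the aim of "detecting a 50% reduction in the cumulative proportion of subjects who experience BV recurrence by 12 weeks". No 24-week rate is given in either document.

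**The concern.** BV status is scheduled to be assessed at clinic visits on Days 28, 56, 84 and 168. A recurrence is therefore known only to lie between two assessments. Replacing that interval by its midpoint and treating it as an observed time ties the quantiles to the visit calendar. The effect is greatest in the 12-week gap between Visits 4 and 7, where the only scheduled contacts are telephone interviews.

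Two things are at stake. First, the long-term objective is efficacy as compared to placebo, yet the time-to-event analysis describes each arm separately and compares nothing. Second, the chosen summary is a quantile that the plan's own rates do not reach by Week 12, so most of Table 17 would read as not estimable. A comparison added after unblinding would be a post hoc choice.

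**Working it through.** **Inputs.** From SAP 5: recurrence of 0.30 and 0.15 at Week 12; "this trial is powered at the 70% level"; "LACTIN-V to placebo allocation ratio of 2:1 and 10% of subjects drop-out from the Complete Case population"; N = 228. From SAP 6.1: "For all tests, a 5% two-sided significance level will be used". From SAP 4.1: visits at Weeks 4, 8, 12 and 24. From Protocol 7.3 to 7.8: clinic visit windows of ±7 days.

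**The plan's own figure.** Pooled-variance formula with p̄ = (0.30 + 2 × 0.15)/3 = 0.20:

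n(placebo) = [1.96·√(1.5 × 0.20 × 0.80) + 0.524·√(0.30 × 0.70 + 0.15 × 0.85/2)]² / 0.15² = 67.7, so 68.

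68/0.9 = 75.6, so 76; 76 × 3 = 228. The stated N is reproduced. Expected complete cases are about 68 placebo and 137 LACTIN-V.

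**12-week quantiles at the planning rates** (exact binomial, complete cases):
- Placebo median needs 34 of 68: P(Bin(68, 0.30) ≥ 34) = 0.0004.
- LACTIN-V median (69 of 137 at 15%): effectively 0. Third quartile: effectively 0 in both arms.
- LACTIN-V first quartile needs 35 of 137: P(Bin(137, 0.15) ≥ 35) = 0.0009.
- Placebo first quartile needs 17 of 68: probability 0.85. In simulation it usually falls at the Day 70 midpoint, (56 + 84)/2.

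**24 weeks.** With no stated rate, I assume a constant hazard.
- Placebo: λ = −ln(0.70)/84 = 0.00425 per day; true median ln 2/λ = Day 163; recurrence by Day 168 is 1 − 0.70² = 51.0%.
- LACTIN-V: 1 − 0.85² = 27.75%.
- Placebo median reached: P(Bin(68, 0.51) ≥ 34) = 0.61. LACTIN-V median reached: about 2 × 10⁻⁸.
- With visits on schedule, a first positive at Visit 7 after a negative Visit 4 is dated (84 + 168)/2 = Day 126.
- In simulated placebo arms with ±7-day windows, the median was estimable in about 62% and centred on Day 128.5 (5th to 95th percentile, Days 125 to 132). That is about five weeks before Day 163.
- With a log-log confidence interval, the upper limit was open in more than 90% of the arms that had a median.

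**Sensitivity of the 24-week result.** If the placebo hazard in Weeks 12 to 24 is a multiple of the earlier hazard:

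| Multiple | Placebo recurrence by Week 24 | P(median reached) |
|---|---|---|
| 1 | 51% | 0.61 |
| 0.9 | 49% | 0.50 |
| 0.75 | 46% | 0.32 |
| 0.5 | 41% | 0.10 |

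If 30% of the recurrences between Visits 4 and 7 were instead diagnosed at unscheduled visits at onset, the simulated median still centred on Day 127.5. If the Day 140 telephone call counted as an observed time point, the midpoint would be (140 + 168)/2 = Day 154.

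**What a comparison could deliver.** Under constant hazards HR = ln(0.85)/ln(0.70) = 0.456. Expected events are 68 × 0.30 + 137 × 0.15 = 41 by Day 84, and 68 × 0.51 + 137 × 0.2775 = 73 by Day 168. By Schoenfeld's formula the log-rank power is about 66% and 88%.

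**The case against.** The strongest reply is that this is an additional analysis in a screening Phase II-b trial, and that the arms are compared elsewhere. Tables 11 and 12 give cumulative recurrence by Weeks 12 and 24 with odds ratios and chi-square tests. Tables 13 to 16 do the same at each visit, and the exploratory Poisson and repeated-measures models also compare arms. The protocol promised a time-to-event analysis, not a time-to-event test. Midpoint dating follows the same schedule in both arms and does not change cumulative recurrence at the visits.

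Most of that stands, and it limits the weight of the point. It does not close the gap. Tables 13 to 16 count women positive at a given visit among those who returned, not cumulative risk. Tables 11 and 12 cover two time points and do not use censoring. None is a time-to-event comparison.

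A reader might infer more than the documents support:
- *Only medians are reported.* The median's interval, quartiles, range, counts and curves are also planned.
- *The 24-week median near Day 126 follows from the plan's own rates.* It needs an assumed hazard, concerns placebo only, and sits on the 50% line. If placebo recurrence were in the upper part of the 20–75% range cited in SAP 2, medians could exist and fall earlier.
- *The confidence interval would be falsely narrow.* Under the same model the upper limit is usually open, so the interval would show the uncertainty.
- *Every recurrence between Visits 4 and 7 is dated near Day 126.* Unscheduled visits may include Amsel and Gram-stain testing (Protocol 7.10). SAP 6.3.2 dates some recurrences at discontinuation for lack of effect or at the start of other BV treatment.

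**Conclusion.** The point holds as a limited, worthwhile improvement to a secondary analysis. Two parts need no assumption beyond the documents: there is no between-arm time-to-event estimate or test, and at 30% versus 15% a 12-week median is not estimable in practice in either arm (0.04% for placebo, effectively zero for LACTIN-V). LACTIN-V would almost never reach even its first quartile by Week 12.

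The 24-week part is conditional. Under constant hazard a placebo median would appear in about 61% of trials, and the visit schedule would place it roughly five weeks early. LACTIN-V would have none. That result also depends on reading the previous observed time point as the last BV assessment, which the SAP does not define. Nothing here touches the primary chi-square test or its sample size.

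**What to change.** Before unblinding, revise SAP 8.2, the time-to-event code in SAP 6.1.1, Tables 17 and 18, and Figures 2 and 3:

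1. Lead with cumulative recurrence at Weeks 4, 8, 12 and 24 by arm, each with a 95% confidence interval, and the between-arm difference with its interval. Use an interval-censored estimator (for example PROC ICLIFETEST) or a life-table on the visit schedule.
2. Add an interval-censored or discrete-time log-rank test.
3. Define the previous observed time point as the last BV assessment with both Amsel and Nugent results, so that telephone contacts do not count.
4. Report a median only if it is reached, and then as the visit interval that contains it.

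The cost is a different SAS procedure and new shells for two tables and two figures. No new data are needed.
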